## 6 Trial Conduct

### 6.1 Subject Disposition and Reasons for Discontinuations

Subject disposition is summarized for the randomized sample. Disposition is summarized by treatment group and by subgroup of gender, age ( $< 65$ ;  $\geq 65$  and  $< 75$ ; or  $\geq 75$ ), race, and region (North America or Other).

Reasons for discontinuation will be summarized for the randomized sample by treatment group and by subgroup of gender, age, race, and region.

### 6.2 Treatment Compliance

Compliance in taking investigational medicinal product is calculated by dividing the number of tablets taken by the total number of tablets the subjects were scheduled to take during the trial period. For lost-to-follow-up subjects, last IMP end date record will be used as the treatment end date.

Number (%) of subjects meeting compliance cut-offs ( $< 70\%$ ,  $\geq 70\%$  and  $< 80\%$ ,  $\geq 80\%$  and  $< 90\%$ ,  $\geq 90\%$ ) will be summarized by treatment group.

### 6.3 Protocol Deviation

Protocol deviations are summarized by center and type of deviation for randomized subjects by treatment group. A listing of protocol deviations will also be generated.

## 7 Baseline Characteristics

### 7.1 Baseline Definition

For analyses of the double-blind treatment period data, the baseline is the Baseline measurement (expected to be at Day 0). Baseline measurement is defined as the last available measurement prior to the start of double-blind IMP.

## 7.2 Demographic Characteristics

Baseline demographic characteristics including age, gender, race, ethnicity, height, weight, waist circumference, and body mass index (BMI) will be tabulated by treatment group for all randomized subjects. Additional summaries by the following subgroups will be also generated: by gender, by age group (< 65;  $\geq$  65 and < 75; or  $\geq$  75), by race, and by region (North America or Other).

Mean, range and standard deviation will be used to describe continuous variables such as age. Frequency distributions will be tabulated for categorical variables such as race.

## 7.3 Disease History

A summary of medical, psychiatric, neurological (excluding Alzheimer's), and Alzheimer's disease history will be presented for the Randomized Sample (by treatment group and overall).

## 7.4 Baseline Disease Characteristics

For the Randomized Sample, baseline and baseline disease characteristics will be summarized by treatment group and overall. The following baseline characteristics will be summarized at baseline: number (%) of institutionalized / non institutionalized subjects; CMAI total score; CMAI derived agitation factors of aggressive behavior, physically nonaggressive behavior, and verbally agitated behavior; Clinical Global Impression-Severity of Illness Scale (CGI-S) score, [REDACTED]

[REDACTED] Mini Mental State Examination (MMSE) score; Sheehan Suicidality Tracking Scale (Sheehan-STS) score.

Number of subjects with presence of psychotic symptoms will be summarized at baseline using [REDACTED]

## 8 Efficacy Analysis

All efficacy analyses pertaining to the double-blind treatment period will be performed on the Efficacy Sample, and subjects will be included in the treatment group as randomized.

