7.2 Datasets for Analysis

The following samples are defined for this trial:

- Randomized: consists of all subjects who were randomized into this trial
- Safety: consists of all subjects who were administered at least 1 dose of IMP
- Efficacy: The intent-to-treat (ITT) population consists of all subjects in the randomized sample who took at least 1 dose of IMP (brexpiprazole or placebo), have a baseline, and at least 1 postbaseline evaluation for the CMAI total score.

In general, baseline of an efficacy endpoint is defined as the last observation of the endpoint before the subject is randomized.

The core dataset for all efficacy analyses is based on the ITT population, which is defined in the efficacy sample above. As will be described below, in order to handle missing data and restrictions imposed by different types of analyses (eg, change from baseline analysis), datasets derived from the ITT population will be used for the efficacy analysis.

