## 5 Data Sets and Missing Data

### 5.1 Data Sets for analysis

The following analysis samples are defined for this trial:

**Randomized Sample:** Consists of all subjects who were randomized into this trial. Subjects are considered randomized when they are assigned a treatment number by the eSource method at the end of Screening Period. A subject receiving trial treatment outside of the eSource will not be considered randomized, but safety will be reported.

**Safety Sample:** Consists of all subjects who were administered at least one dose of IMP. Subjects will be excluded from this population only if there is documented evidence (ie, number of tablets dispensed = number of tablets returned or no trial drug dispensed) that the subject did not take trial drug. If a subject is dispensed investigational medicinal product (IMP) and is lost to follow-up, he/she will be considered exposed.

**Efficacy Sample:** The intent-to-treat (ITT) population consists of all subjects in the randomized sample, who took at least 1 dose of IMP and have a baseline and at least one post-baseline evaluation for the CMAI total score.

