#### 8.1.4 Sensitivity Analyses for the Primary Efficacy Endpoint

Traditionally the dropout mechanisms are divided into three types: (1) Missing Completely at Random (MCAR), in which the probability of dropout doesn't depend on the observed data and the missing data; (2) MAR, in which the probability of dropout depends on the observed data; and (3) MNAR, where the probability of dropout depends on the missing data and possibly the observed data.

Most of MNAR methods have treated all observations with dropout as if they fall within the same dropout type. In practice, we would find that different dropout reasons may be related to the outcomes in different ways, for example, detailed dropout reasons for this trial are: adverse events (AE), lost to follow-up, protocol deviation, sponsor discontinued trial, subject met (protocol-specified) withdrawal criteria, subject was withdrawn from participation by the investigator, and subject withdrew consent to participate. Dropout due to an AE may lead to MNAR dropout. Subject withdrew consent may also lead to MNAR dropout. However, it is debatable whether a dropout caused by subjects withdrew consent is MAR or MNAR. Except AE, and subject withdrew consent, all other dropout reasons may be assumed as either MCAR or MAR dropout.

As sensitivity analyses for MAR assumption, analyses for MNAR will be carried out. Pattern Mixture Models (PMM) based on Multiple Imputation (MI) with mixed missing data mechanisms will be used to investigate the response profile of dropout subjects by last dropout reason under MNAR mechanism for the following three scenarios:

- Dropout reasons due to AE as MNAR
- Dropout reasons due to either AE or subject withdrew consent as MNAR
- All dropouts as MNAR

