### **Placebo Based Imputation Methods**

Similar to the “Standard” multiple imputations, except parameters for imputation model obtained from only the placebo (control) group. Missing data for both placebo and drug group are imputed based on the imputation model derived from placebo data. If drug improved outcomes prior to dropout, this benefit is carried into subsequent imputed values, but will diminish over time in accordance with the correlation structure.

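### The MNAR sensitivity analyses omit dosed subjects with no post-baseline CMAI, so the all-dropouts scenario does not cover every dropout; the likely effect is small

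*SAP*

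**What the plan says.** SAP Section 8 sets one population without exception: "All efficacy analyses pertaining to the double-blind treatment period will be performed on the Efficacy Sample". SAP 5.1 defines that sample, under the intent-to-treat label, as randomised subjects "who took at least 1 dose of IMP and have a baseline and at least one post-baseline evaluation for the CMAI total score". Protocol 7.2 carries the same condition ("have a baseline, and at least 1 postbaseline evaluation for the CMAI total score") and adds that "The core dataset for all efficacy analyses is based on the ITT population".

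SAP 8.1.4 describes the checks on the missing-at-random assumption. Pattern-mixture models with multiple imputation "will be used to investigate the response profile of dropout subjects by last dropout reason under MNAR mechanism", in three scenarios, the broadest being "All dropouts as MNAR". Two methods follow:

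- **Delta adjustment.** Step 3 adds delta to the post-dropout values of treated subjects who left because of an adverse event or withdrawn consent. Delta runs up to 100% of 6.5 points and/or of the observed difference.
- **Placebo-based imputation.** Here "Missing data for both placebo and drug group are imputed based on the imputation model derived from placebo data".

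Neither method names a population other than the Efficacy Sample.

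On early leavers, protocol 3.8.3.2 requires Week 12 or ET evaluations at withdrawal, and SAP 8.1.3 includes ET visits before Week 12 by visit window. SAP 8.1.1 expects no ET evaluation after a terminal or lost-to-follow-up event. The first scheduled post-baseline CMAI is at Week 2.

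**The concern.** Requiring a post-baseline score costs nothing in the primary MMRM. That model analyses observed change, and a subject with no post-baseline value contributes no outcome to it.

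Imputation is different. A baseline CMAI and the treatment arm are enough to impute Weeks 2 to 12, so a subject who took study drug and left before any further CMAI could be included. As written, that subject is not. Yet the subject belongs to the target population in SAP 8.1.1 and has had its intercurrent event, which is early discontinuation from any cause.

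At stake is the reach of the stress test. Each omitted brexpiprazole dropout is one that neither the delta nor the placebo-based method can penalise. The tipping point would then look somewhat more robust than it is, and the all-dropouts label would promise more than the analysis delivers.

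**Working it through.** **1. The texts side by side.** Section 8 puts all efficacy analyses on the Efficacy Sample. Section 5.1 requires a post-baseline CMAI for that sample. Section 8.1.4 names no other set. The COVID-19 and opportunity-to-complete analyses (8.1.6, 8.1.8) use the Efficacy Sample or subsets of it, and 8.1.7 only removes sites. Nothing restores a dosed subject who has no post-baseline CMAI.

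**2. Inputs.** Effect 6.5 points, SD 16.5, dropout 12-13%, maximum N about 330 at 2:1, so 220 and 110 (SAP Section 4). The share of dropouts with no post-baseline CMAI is not given and has to be assumed.

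**3. The plan's own figure.** With 200 and 100 subjects, SE = 16.5 × √(1/200 + 1/100) = 2.02. Then 6.5/2.02 = 3.22, and 3.22 − 1.96 = 1.26, which gives power of 89.6% (89.4% with the noncentral t). The stated 89% is reproduced, so 6.5 and 16.5 are sound as a scale.

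**4. Number affected (assumption: dropout even over 12 weeks, no ET CMAI obtained before Week 2).** Share of all subjects e = (2/12) × 12% = 2.0%, or (2/12) × 13% = 2.2%. Of 330 that is 6.6 to 7.2, about 7. Every ET CMAI obtained lowers it.

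**5. Placebo-based shift omitted.** A brexpiprazole subject imputed from baseline with placebo parameters carries no treatment benefit, so adding a share e lowers the contrast by e times its current value. At 6.5 points this is 0.020 × 6.5 = 0.13, or 0.022 × 6.5 = 0.14. Under placebo-based imputation the contrast is already below 6.5, because later dropouts are also drawn towards placebo, so the fall is a little smaller.

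**6. Delta shift omitted, if every brexpiprazole dropout receives 6.5 points.** With dropout D equal in both arms, the shift with all dropouts kept is 6.5 × D = 0.78 to 0.85. On the Efficacy Sample it is 6.5 × (D − e)/(1 − e).

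| Assumed share of dropouts with no post-baseline CMAI | Subjects of 330 | Shift on Efficacy Sample | Shift omitted |
|---|---|---|---|
| 10% | about 4 | 0.71-0.77 | about 0.07 |
| 1/6 (even dropout) | about 7 | 0.66-0.72 | 0.12-0.13 |
| 25% | 10-11 | 0.60-0.66 | 0.18-0.19 |

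The ceiling, with every dropout leaving no post-baseline CMAI, is 40 to 43 subjects. It would require all of them to leave before Week 2 with no ET assessment.

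**7. Scale.** With 12.5% dropout, SE = 16.5 × √(1/96.25 + 1/192.5) = 2.06. The omitted 0.13 point is 0.13/2.06 = 0.06 of a standard error.

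**The case against.** The strongest case against is that few subjects are lost and that a constant population has merit.

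- **ET visits recover many early leavers.** Withdrawn subjects must have ET evaluations, and those scores enter by visit window. This stands. An early adverse-event withdrawal is a case where an ET CMAI is expected. The subjects lost are mainly those with terminal or lost-to-follow-up events, plus adverse-event or consent dropouts who miss the ET assessment. The visit-window table was not in the text available to me, so I could not check how an ET visit before Week 2 is slotted.
- **Loss to follow-up is treated as MCAR or MAR in 8.1.4.** This also stands. For these subjects the omission does not touch the first two scenarios; it bears on the all-dropouts scenario and the placebo-based method.
- **Delta as written would not reach everyone added.** Step 3 covers only adverse-event and consent dropouts. This is correct, and it means a wider data set alone would not deliver an all-dropouts delta analysis.
- **Keeping the primary analysis set isolates the missing-data assumption.** This is a fair preference. It does not excuse a scenario named for all dropouts that excludes some of them, and reporting the number added keeps the two sets comparable.
- **Counts may already be available.** Disposition and reasons are summarised by arm on the Randomized Sample (SAP 6.1). SAP 6.1 does not say that the summary separates those with no post-baseline CMAI.

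**Conclusion.** The point holds as a minor gap in coverage. The delta-adjusted and placebo-based imputations omit randomised, dosed subjects who have a baseline but no post-baseline CMAI, so the all-dropouts scenario is incomplete. Under even dropout of 12-13%, about 2% of subjects or fewer are affected (up to about 7 of 330). About 0.13 point or less is then missing from the placebo-based shift at a 6.5-point effect. The same holds for a 6.5-point delta only if every added brexpiprazole subject receives it. These sizes rest on an assumed timing of dropout and on equal dropout in the two arms; an imbalance between arms could change them.

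Three stronger readings are tempting and not supported:

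- **That the primary result is biased.** The excluded subjects contribute no outcome to an observed-case MMRM on change.
- **That all the earliest dropouts are removed.** Those with an ET CMAI in a visit window are kept.
- **That the loss is large.** To reach 4% of randomised subjects (13 of 330), about one third of all dropouts would have to lack any post-baseline CMAI, and nothing in the documents indicates that.

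**What to change.** In SAP 8.1.4, as an explicit exception to Section 8 (and to the core dataset in protocol 7.2; protocol 7.3 leaves the MNAR details to the SAP):

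- Run the delta-adjusted and placebo-based imputations on all randomised subjects who took at least one dose and have a baseline CMAI, imputing Weeks 2 to 12 where no post-baseline value exists. The imputation model must include baseline CMAI.
- Word step 3 so that in the all-dropouts scenario delta applies to every brexpiprazole dropout, whatever the reason.
- Report the number of subjects added in each arm.

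Leave the primary MMRM and the Efficacy Sample unchanged.

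The cost is a short addition to the SAP, a wider input data set for imputations already planned, and slightly more analysis work. The sensitivity results may come out slightly less favourable. If few subjects are added, the per-arm count will show that the exclusion was harmless.

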## 8.1 Primary Efficacy Analysis

The primary efficacy endpoint is the change from the baseline (Day 0 visit) to the end of the double-blind treatment period (Week 12 visit) in CMAI total score. The null hypothesis is that there is no difference in the mean change from baseline to Week 12 in CMAI total score between the two treatments brexpiprazole and placebo.

The primary analysis will be performed on the Efficacy Sample which includes all randomized subjects who took at least one dose of IMP in the double-blind treatment period and who have both a baseline and at least one post-randomization CMAI total score during the double-blind treatment period.

### 8.1.1 Primary Estimand

In order to support the primary objective of the trial, treatment effect will be estimated under hypothetical situation had no subjects discontinued early from treatment. Due to this strategy, the last collected efficacy assessment after premature trial discontinuation will be done only once at the Early Termination (ET) Visit. Every effort will be made to complete all the ET evaluations prior to administering any additional medications for the treatment of agitation or any other prohibited medications. In the case of terminal or lost to follow-up event, no ET evaluations would be expected, and only scheduled assessments performed before such an event would be used for the primary efficacy analysis. All collected efficacy assessments will be slotted as per the Visit Window Definition, and only one assessment per visit window will be used for the primary efficacy analysis. If there are multiple assessments available in the same window, the latest one will be used.

This trial seeks to clarify the efficacy of brexpiprazole in improving the CMAI total score in the idealistic scenario of full adherence to the assigned treatment in all subjects. In clinical trial practice, however, instances of non-adherence such as treatment discontinuation are likely to occur before the study endpoint (i.e., the Week 12 Visit for this trial). Given this consideration, the hypothetical estimand is the most appropriate for achieving the primary objective of the trial. The primary estimand is described by five attributes as follows.

- Target Population: Subjects with agitation associated with dementia of the Alzheimer's type who have met protocol inclusion/exclusion criteria

- Endpoint: Change from Baseline to Week 12 in the CMAI total score
- Intercurrent Events: Intercurrent events refer to premature treatment discontinuation (i.e., early dropout) prior to Week 12 attributable to adverse events or lack of efficacy or withdrawal of consent/assent or any other causes.
- Measure of Intervention effect: Difference in endpoint means between the brexipiprazole and placebo treatment arm.
- Treatment regimen: 2 or 3 mg daily for 12 weeks.

During the course of this trial, the COVID-19 pandemic broke out. The pandemic had a significant impact on many aspects of clinical trials. There are occasionally virtual visits (i.e., remote assessments) and possibly early discontinuation of treatment directly or indirectly related to the pandemic. However, subjects were required to attend the screening, Day 1 and the end of trial visits in person (i.e., face-to-face). Note that virtual visits in the pandemic environment will not be treated as an intercurrent event for the primary analysis. Subjects who drop out with a reason relating to the COVID-19 pandemic will be handled as they would have dropped out for another reason if the pandemic had not happened.

The hypothetical strategy of handling intercurrent events will be used to clarify the efficacy of the brexipiprazole had there be no occurrence of intercurrent events, regardless of being COVID-19 related or not. In other words, the estimand as described above will use the hypothetical strategy to address the treatment effect of interest that would be envisioned under the hypothetical setting of no occurrence of intercurrent events in the planned 12-week treatment period.

The estimator will be the Mixed Model Repeated Measurements (MMRM) estimate for treatment difference at Week 12, based on all observed case (OC) data until discontinuation from the trial. This reflects the chosen strategies for the identified intercurrent events. Details of the model is provided in the next section.

The OC data consist of actual observations recorded at each visit during the double-blind treatment period. The term “OC data” means that longitudinal data, if missing, will not be imputed by applying an imputation rule (e.g., the LOCF rule). For example, if the subject had a missing CMAI total score at Week 12, then his score at Week 12 will not be imputed with his score observed at an earlier visit. Note that in this SAP the OC data will be used as input data for all the MMRM analyses, though “OC” is not explicitly mentioned.

### 8.1.2 Method of the Primary Analysis

Mean change from baseline in CMAI total score will be analyzed using a restricted maximum likelihood (REML)-based repeated measures approach. The analysis will be performed by fitting the MMRM model with an unstructured (UN) variance-covariance structure in which the change from the baseline in CMAI total score (Week 2, 4, 6, 8, 10, 12) will be the dependent variable based on the OC data. The analysis will include treatment (brexpiprazole and placebo), trial center, visit week, and an interaction term of treatment by visit week as the fixed, categorical effects and include the interaction term of baseline CMAI total score by visit week as covariates. In case there is a convergence problem with the MMRM model with the UN variance-covariance matrix, the following structures will be used in the order of 1) heterogeneous Toeplitz (TOEPH), 2) heterogeneous autoregressive of order 1 (ARH1), and 3) heterogeneous compound symmetry (CSH) and the first variance-covariance structure converging to the best fit will be used as the primary analysis.

The Kenward-Roger approximation will be used to estimate denominator degree of freedom and adjust standard errors. The contrast (i.e., difference in least-square means between brexpiprazole and placebo) at the Week 12 visit will be estimated from the interaction term of treatment by visit week and will serve as the primary treatment comparison. The point estimate and the 95% confidence interval estimate of the contrast at the Week 12 visit will be reported. Significance test will be based on the contrast estimate at the Week 12 visit by using a two-sided 0.015 level for the interim analysis and a two-sided 0.035 level for the final analysis (when the trial does not stop at the interim analysis). Analysis will be implemented using the software Statistical Analysis System® (SAS® version 9.4 or later) procedure PROC MIXED.

If a structured variance-covariance is used, the empirical sandwich estimator of the standard error of the fixed effects parameters will be used in order to deal with possible model misspecification of the variance-covariance matrix.

Small centers will be defined as centers that do not have at least one evaluable subject (evaluability with regard to the primary efficacy variable) in each treatment arm in the double-blind treatment period. All small centers will be pooled within region to form “pseudo centers” for the purpose of analysis according to the following algorithm. Small centers will be ordered from the largest to the smallest based on the number of evaluable subjects. The process will start by pooling the largest of the small centers with the smallest of the small centers until a non-small center is formed. This process will be repeated using the centers left out of the previous pass. In case of ties in center size, the center with the smallest center code will be selected. If any centers are left out at the end

[figure not shown]
of this process, they will be pooled with the smallest pseudo centers, or if no pseudo centers exist, they will be pooled with the smallest non-small center. The pooling of the small centers will be performed within each region (North America and Other).

The chosen MMRM analysis assumes missing data to be “missing at random” (MAR), which is a reasonable assumption in longitudinal clinical trials. However, the possibility of “missing not at random” (MNAR) data can never be ruled out. In order to further evaluate robustness of the primary results to the deviations from MAR assumptions, additional sensitivity analysis will be conducted. Sensitivity analyses based on selection model, pattern-mixture model, and/or shared parameter model will be performed in order to explore data missing mechanisms of MNAR and investigate the response profile of dropout reason.

In case of gross violations of the MMRM model assumptions, additional supportive analyses will be provided using the generalized version of the Cochran-Mantel-Haenszel (CMH) procedure (van Elteren test), controlling for trial site.

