## **8.2 Key Secondary Analysis**

The key secondary efficacy variable is the change from baseline to Week 12 in the CGI-S score, as related to agitation. It will be analyzed by the same statistical methodology specified for the analysis of the primary efficacy variable. In order to control the overall

type I error rate for this key secondary efficacy analysis, a hierarchical testing procedure will be used so that the overall experiment-wise type I error rate is maintained. Thus, if the primary efficacy analysis for the CMAI total score yields a statistically significant result for the comparison of brexpiprazole versus placebo, then the corresponding comparison for this key secondary efficacy variable (CGI-S score) will be tested.

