## 8.5 Interim Analysis

An IA of the efficacy data will be performed by an independent DMC when approximately 255 subjects have completed the 12-week trial or discontinued early from the trial. The sponsor will remain blinded to the IA results and will only receive DMC's recommendation as per the IAP and the DMC charter. The DMC may recommend stopping the trial for efficacy or for futility or continuing the trial to the final analysis.

To control the overall Type-I error rate at 0.05 level (two-tailed) in a strong sense, a conservative Bonferroni critical boundary will be used for this two-stage group sequential trial. Specifically, the significance level for the IA is set at 0.015 (2-sided) and the significance level for the final analysis (if the trial does not stop at the IA) is set at 0.035 (2-sided). The IA will be performed as pre-specified in the IAP.

If the DMC recommends stopping the trial for overwhelming efficacy at the conclusion of IA, the sponsor intends to halt the trial in two weeks after receiving DMC's recommendation. The MMRM analysis for the primary endpoint will be repeated on all available data including the data newly accrued after the IA database lock. A significance

level of 0.05 (two-sided) will be used for this additional analysis. All on-going subjects will be given a chance to rollover to the active treatment extension trial Trial 331-201-00182.

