significant at the pre-specified level, then statistical significance on the key secondary endpoint will be claimed and the testing will proceed down to test the CMAI subscale score (aggressive behavior). If neither of these two tests is nominally significant, then statistical significance on the key secondary endpoint cannot be claimed and testing will stop. Testing for each of the other secondary endpoints in the above sequence from 3) to 5) will be conducted similarly to that of key secondary endpoint. Specifically, one test will be conducted on the IA data at a two-sided 0.015 level and the other will be on all available data at a two-sided 0.035 level. Decision rules regarding whether to claim statistical significance and whether to stop the testing will be similar as in the case of testing the key secondary endpoint.

If the trial does not stop at the IA, the above sequence of testing from 1) to 5) will be repeated for the final analysis with the use of a two-sided 0.035 level. In this scenario, the final analysis will be conducted using the data of approximately 330 subjects. There will be no data accrual after the database lock for the final analysis.

Below is the flowchart illustrating the above multiple testing procedure:

For completeness of the presentation, all unadjusted (unadjusted for multiplicity)  $p$ -values will be reported regardless of whether the endpoints are nominally significant or not.

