## 2 Modification to the Multiplicity Adjustment

The hypotheses of interest for the planned labeling will be comprised of only the primary endpoint CMAI total score and the key secondary endpoint CGI-S score. The hypotheses pertaining to all other secondary endpoints will be excluded from the hierarchical testing procedure.

The testing will be conducted on two hypotheses of interest in the order specified below:

- 1) The primary efficacy endpoint, change from baseline to Week 12 in the CMAI total score
- 2) The key secondary efficacy endpoint, change from baseline to Week 12 in the CGI-S score

After reviewing the unblinded interim analysis results, DMC recommended that the trial be continued to the planned end. As a result, at the final analysis, the primary efficacy endpoint will be tested at a two-sided 3.5% significance level, and upon achieving significance on the primary endpoint, the key secondary endpoint will be tested at the same level. The hierarchical testing procedure controls the Type-I error rate for both the primary efficacy endpoint and the key secondary efficacy endpoint.

This page is a manifestation of an electronically captured signature

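### The SAP reports a 95% confidence interval for the Week 12 contrast, but the final CMAI and CGI-S tests run at two-sided 0.035, so interval and test can disagree

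*SAP*

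**What the plan says.** SAP Section 8.1.2 describes the estimate and the test of the primary contrast in consecutive sentences. On the estimate: "The point estimate and the 95% confidence interval estimate of the contrast at the Week 12 visit will be reported". On the test, significance is judged at 0.015 two-sided at the interim and at "a two-sided 0.035 level for the final analysis (when the trial does not stop at the interim analysis". Section 8.5 gives the same two levels.

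For CGI-S, Section 8.2 says: "It will be analyzed by the same statistical methodology specified for the analysis of the primary efficacy variable". The SAP addendum on multiplicity (its Section 2) reports that the DMC recommended continuing to the planned end. It sets the final CMAI test at two-sided 3.5% and says that, if the primary succeeds, "the key secondary endpoint will be tested at the same level". The addendum's introduction leaves the rest of the statistical methodology as it was.

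Section 8.6 adds that p-values unadjusted for multiplicity "will be reported regardless of whether the endpoints are nominally significant or not". The text supplied contains no 96.5% interval, no repeated confidence interval, and no statement that the 95% interval is nominal.

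**The concern.** A two-sided 95% interval excludes zero exactly when the two-sided p-value is below 0.05. The plan declares success only at 0.035 or below. For any p-value between the two, the display shows an interval clear of zero for a contrast that has not met its criterion.

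The one place where the plan tests the primary endpoint at 0.05 is the re-test on all data after an efficacy stop at the interim (SAP Sections 8.5 and 8.6). That branch did not occur, so 0.05 no longer matches any confirmatory test in the trial.

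The risk is misreading. A CMAI p-value of 0.04 would be printed beside an interval excluding zero, and readers who judge from intervals would take a failed confirmatory test as positive. The same holds for CGI-S, the only other endpoint left in the testing hierarchy. If the level is not fixed in advance, the choice of which interval to feature could also be made after the p-value is known.

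**Working it through.** **Inputs.** Effect 6.5 points, SD 16.5, 2:1 allocation, initial N 300, maximum N about 330, interim at about 255, dropout 12-13% (SAP Sections 3 and 4). Levels 0.015 and 0.035, two-sided (SAP Section 8.5). Information fraction 255/330 = 0.77 (SAP Section 8.7). Assumption: 12.5% dropout, which leaves 330 × 0.875 ≈ 289 evaluable.

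**1. The plan's own figures.** At N = 300, SE = 16.5 × √(1/200 + 1/100) = 2.021 and 6.5/2.021 = 3.217. Power at 0.05 is Φ(3.217 − 1.960) = 0.896, in line with the stated 89%. The levels add up: 0.015 + 0.035 = 0.05. With critical values 2.432 and 2.108, two-stage power is 87.0% for looks at 255 and 300 subjects, 85.8% for 330 with 12.5% dropout at both looks, and 90.1% for 330 without dropout. The stated 87% is reproduced on the first basis and is close on the second.

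**2. Matching interval.** The level that inverts the final test is 1 − 0.035 = 96.5%. Its multiplier is 2.108 against 1.960, a ratio of 1.076, so it is 7.6% wider.

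**3. Where interval and test disagree.** SE = 16.5 × √(1/(2n/3) + 1/(n/3)). An interval excludes zero when the observed difference exceeds its half-width, so the two half-widths are the ends of the disagreement band.

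| Evaluable | SE | 95% half-width | 96.5% half-width | Gap per side |
|---|---|---|---|---|
| 330 | 1.93 | 3.78 | 4.06 | 0.29 |
| 289 | 2.06 | 4.04 | 4.34 | 0.31 |

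**4. How often.** The event is continuing past the interim and then landing in the band: P(|Z1| < 2.432 and 1.960 < |Z2| < 2.108), where the two statistics correlate at √(255/330) = 0.879. Dividing by P(continue) gives the probability conditional on continuation. The non-binding futility rule is ignored here.

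| True difference | Evaluable | Overall | P(continue) | Given continuation |
|---|---|---|---|---|
| 6.5 | 330 | 2.2% | 0.297 | 7.4% |
| 6.5 | 289 | 2.9% | 0.366 | 7.8% |
| 4.5 | 330 | 5.1% | 0.648 | 7.9% |
| 4.5 | 289 | 5.3% | 0.696 | 7.7% |
| 0 | either | 1.4% | 0.985 | 1.4% |

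If the futility rule is followed, the conditional figures at 6.5 points become 7.6% and 8.2%. The null row counts both directions; about 0.7% favours the drug.

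**5. Joint coverage over both looks.** P(|Z1| < 2.432 and |Z2| < c) under the null is 96.1% for c = 2.108 (98.5% interval at the interim, 96.5% at the final) and 94.7% for c = 1.960 (95% at the final). Exactly 95% needs c = 1.988, a 95.3% final interval. The Bonferroni split therefore spends about 100 − 96.1 = 3.9% of the 5%. The SAP itself calls the boundary conservative, and the error rate is controlled.

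**The case against.** The strongest reply is that nothing is decided on the interval. Section 8.1.2 ties significance to the test, and 0.035 is repeated throughout the SAP and its addendum. That is correct, and it limits the point to reporting.

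Second, the 95% interval is a reasonable measure of uncertainty in its own right. With it, joint coverage over both looks is 94.7%, nearer to 95% than the 96.1% obtained with a 96.5% final interval. Most of the mismatch comes from a conservative split of alpha, not from an interval that understates uncertainty. This stands, and it is a good reason to keep the 95% interval on display. It does not make that interval agree with the test printed beside it.

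Third, 95% is the level used for the COVID-19 sensitivity analyses in SAP Section 8.1.6, so a 96.5% interval alone would not compare like with like. This also stands, and showing both intervals meets it.

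Fourth, Section 8.6 already describes the p-values as unadjusted, and the band is only about 0.3 points wide. But that label covers p-values, not intervals, and once the trial has continued the event has roughly a 1 in 13 chance at the design effect.

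Fifth, the lists of summary tables and the interim table outputs are not in the public text, so a footnote or second interval there cannot be ruled out. The CGI-S part is also a reading of Section 8.2, since the interval sentence concerns the primary contrast. Both are fair limits on the claim.

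**Conclusion.** The point holds as a reporting mismatch of modest weight. The 95% level in Section 8.1.2 matches neither the interim nor the final test, and the addendum makes 0.035 the level that applies. It does not touch type I error, power, the estimand or the decision rule.

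The sizes rest on the planning SD of 16.5, normal critical values, exact 2:1 allocation and 12.5% dropout for the lower sample size. They ignore precision gained from the baseline covariate and from partial data on dropouts. Those would move the band in CMAI points but not the 7.6% ratio of widths. For CGI-S the supplied text gives no SD or assumed effect, so no band in scale points can be stated; the ratio is the same. The wording of Section 8.1.2 is certain. The absence of a second interval or a label is established only for the text supplied.

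**What to change.** Leave the 0.035 level as it is. Add one sentence to a SAP addendum: at the final analysis, the interval accompanying the tests of CMAI total score and CGI-S is the 96.5% confidence interval, and the 95% interval is also shown, labelled nominal and descriptive. Keeping the 95% column preserves comparison with the sensitivity analyses. This should be settled before unblinding, so that the level is not chosen with the p-value in view.

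The cost is that sentence and one extra column in two tables. The downside is a lead interval about 0.3 CMAI points wider on each side, and two intervals that readers must tell apart. Labelling the existing 95% interval as nominal, without adding the other, would be a smaller step; it would warn the reader but still leave no interval that agrees with the test.
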